#### **4 SUBJECT REGISTRATION**

All subjects must be registered and randomized through the Hoosier Cancer Research Network (HCRN) electronic data capture (EDC) system OnCore. A subject is considered registered when an "On Study" date is entered into OnCore. Subjects must be registered prior to randomization. Subjects must begin therapy **within 5 business days** of randomization.

#### 4.1 STRATIFICATION FACTORS

Subjects will be stratified based on serum total alkaline phosphatase at baseline and extent of disease (described below). Randomization will occur within stratification group.

- Extent of Disease: <6 skeletal metastases with no visceral metastases versus  $\geq 6$  skeletal metastases or visceral metastases.
- Serum total alkaline phosphatase at baseline: Normal vs Abnormal. Abnormal alkaline phosphatase is defined as > 130 IU/L.
- Early Induction or Late Induction status will not be a stratification criterion.

### 5 TREATMENT PLAN

#### 5.1 Treatment schedule

Subjects will be randomized in a 2:1 ratio in favor of the experimental arm to one of the following treatments:

- Arm A (Control): LHRH agonist/antagonist + bicalutamide
- Arm B (Experimental): LHRH agonist/antagonist + bicalutamide + radium-223 dichloride

#### 5.2 Androgen Deprivation Therapy

- All subjects will receive androgen deprivation therapy with a LHRH agonist (any LHRH agonist such as leuprolide acetate or goserelin acetate is acceptable) or a LHRH antagonist (degarelix) or bilateral orchiectomy per the treating physician. Androgen Deprivation therapy with LHRH agonist or LHRH antagonist will be given continuously.
- LHRH Agonist will be given as approved for androgen deprivation at a dose necessary to maintain castrate levels and equivalent to 22.5 mg of Leuprolide IM every 3 months. One, three, four and six month or one year depot injections are acceptable.
- If LHRH Antagonist (Degarelix) is chosen as the method of androgen deprivation therapy, it will be given as approved: Initial, 240 mg subcutaneously given as 2 injections of 120 mg each and subsequent maintenance doses of 80 mg subcutaneously every 28 days.
- A delay of up to 7 days in administering a scheduled dose of LHRH agonist or LHRH antagonist is allowed.

#### 5.3 Androgen Receptor Antagonist

All subjects will receive bicalutamide. Subjects may start bicalutamide within 14 days prior to starting a LHRH agonist/antagonist or the date of bilateral orchiectomy at the discretion of the treating investigator to prevent a clinical flare reaction. Subjects on other anti-androgens prior to registration must switch to bicalutamide without lead-in.

#### 5.4 Radium-223 dichloride

- Radium-223 dichloride is an alpha particle emitter with a physical half-life of 11.4 days. The product is isotonic and has a pH of 6.0-8.0. The radioactive concentration at the reference date is 1,100 kBq/mL. The product has a pre-calibration of 14 days. When administered on a day other than the reference day, the volume should be corrected according to the physical decay table accompanying each shipment.

- The volume per vial is 6 mL, corresponding to 6.6 at the reference day. Radium-223 dichloride has a shelf life of 28 days from production day, when stored at ambient temperature. The shelf life has been demonstrated for temperatures from cold storage (2-8°C) up to 40°C. In addition, it has been shown that the product quality is not jeopardized upon freezing
- Current NIST standard: Radium-223 dichloride, 55 kBq/kg body weight, will be administered as a bolus intravenous (IV) injection (up to 1 minute) at intervals of every 28 days for up to 6 cycles. Subjects randomized to this arm will begin treatment on C2D1.
- The dose of radium-223 dichloride will be recalculated prior to each dose and will be based on the most recent actual body weight, recorded within 4 weeks.
- There must be a minimum of 25 days between consecutive radium-223 dichloride doses.
- The following hematologic criteria must be met within 3 days prior to first dose of Radium 223:
  - ANC  $\geq$  1.5 K/ mm^3
  - Platelets  $\geq$  100 K/mm^3
  - Hemoglobin  $\geq$  8 g/dL (80 g/L) without PRBC transfusion
- The following hematologic criteria must be met within 3 days prior to administration of remaining doses:
  - ANC  $\geq$  1.0 K/ mm^3
  - Platelets  $\geq$  50 K/mm^3
  - Hemoglobin  $\geq$  8 g/dL (80 g/L) with or without PRBC transfusion
- Infusions of radium-223 dichloride may be given within a window of -3 days to +7 days for reasons including observed holidays, inclement weather, scheduling conflicts, etc. Schedule changes should be clearly documented in the source documents and electronic case report forms. Please see Decay Factor Table if date of radium-223 dichloride changes from originally planned.

## 5.5 Designation of Cycle 1 Day 1 date

Cycle 1 Day 1 is designated as the day the subject receives LHRH agonist or antagonist (androgen deprivation therapy) or the date of bilateral orchiectomy. The early induction subjects will have already received their first LHRH agonist or antagonist injection or had bilateral orchiectomy. Please verify this date for early induction subjects with source documentation.

### 5.5.1 Treatment schedule Arm A (Control)

AGENT	DOSE	ROUTE	DAYS
LHRH agonist/antagonist	As per treating physician See 5.2	According to package insert	According to package insert
Bicalutamide	50 mg	Oral (PO)	Daily

### 5.5.2 Treatment schedule Arm B (Experimental)

AGENT	DOSE	ROUTE	DAYS
LHRH agonist/antagonist	As per treating physician See 5.2	According to package insert	According to package insert
Bicalutamide	50 mg	Oral (PO)	Daily
Standard for Radium-223 dichloride	55 kBq (1.5 microcurie) per kg body weight	Intravenous (IV bolus)	Every 28 days for 6 injections

### 5.5.3 Continuation of ADT/completion of Radium-223

After the completion of seven cycles of ADT, further treatment with androgen deprivation will be up to the treating physician. If radium-223 dichloride doses have been delayed for any reason and all 6 doses have not been administered by the 28 weeks' time-point, they may be administered later at the discretion of the site investigator provided laboratory parameters as outlined above are satisfied. The site investigator/site should record data on such delayed radium-223 administrations including dose of radium-223 dichloride, date of administration and hematological parameters obtained within 3 days of administration.

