#### **6.2.2.1 Modifications for Hematologic Toxicity:**

The following hematologic criteria must be met within 3 days prior to first dose of Radium 223:

- ANC  $\geq 1.5$  K/ mm^3
- Platelets  $\geq 100$  K/mm^3
- Hemoglobin  $\geq 8$  g/dL (80 g/L) without PRBC transfusion

The following hematologic criteria must be met within 3 days prior to administration of remaining doses:

- ANC  $\geq 1.0$  K/ mm^3
- Platelets  $\geq 50$  K/mm^3
- Hemoglobin  $\geq 8$  g/dL (80 g/L) with or without PRBC transfusion

If the hematologic parameters listed above are not met:

- Radium-223 dichloride will be held.
- Complete blood counts (CBC) will be measured weekly. Once the counts recover, radium-223 dichloride may resume at the same dose level.
- ADT and bicalutamide will continue without interruption.
- If there is no recovery to these values within 8 weeks after the last administration of radium-223 dichloride, despite receiving supportive care including blood transfusions as clinically indicated, further treatment with radium-223 dichloride will be discontinued. ADT and bicalutamide can continue and the subject will remain on study.

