## 7 STUDY CALENDAR & EVALUATIONS

Early Induction Subjects = Have started ADT prior to being screened for study.

Late Induction Subjects = Have NOT started ADT prior to being screened for this study

Study Day  Induction and Post Induction Cycles = 28 days (4 weeks)  Maintenance Cycles = 84 days (12 weeks)	Screening (0 - 28 days) 	Induction Cycle 1 	Induction Cycles 2-7	Post Induction Cycle 8	Post Induction Cycles 9-12	Maintenance Cycle 13	Maintenance Cycles 14-16 	Maintenance Cycle 17	End of Treatment and Follow up 	
		Day 1	Day 1 (±3)	Day 1 (±7)	Day 1 (±7)	Day 1 (±7)	Day 1 (±14)	Day 28 (±7)	Day 1	
REQUIRED ASSESSMENTS										
Informed Consent	X									
Medical History and Diagnosis/Staging	X									
Physical examination 	X	X	X	X		X		X		
Vital signs including BP, weight, height (screening ONLY) and ECOG PS	X	X	X	X		X		X		
CBC with diff and platelet 	X	X 	X	X		X		X		
CMP, Mag, and Phos. 	X	X 	X	X		X		X		
Alk Phos, PSA 	X	X 	X	X	X	X	X	X	X	
Testosterone 	X	X 		X		X				
AEs & concomitant medications 	X	X	X	X	X	X	X	X	X	
BPI (short form), WHO ladder 		X 	X 	X						
DISEASE ASSESSMENT										
CT or MRI abdomen/pelvis 	X			X		X		X		
Chest X-ray or CT chest if clinically indicated 	X			X		X		X		
CT or MRI Brain if clinically indicated 	X			X		X		X		
Bone Scan 	X			X		X				
DEXA scan 	X					X				
TREATMENT EXPOSURE										
Arm A (Control)										
LHRH agonist/antagonist + Bicalutamide		X	—————→							
Arm B (Experimental)										
LHRH agonist/antagonist + Bicalutamide		X	—————→							
Radium-223 dichloride			X							

Study Day	Screening (0 - 28 days) 	Induction Cycle 1 	Induction Cycles 2-7	Post Induction Cycle 8	Post Induction Cycles 9-12	Maintenance Cycle 13	Maintenance Cycles 14-16 	Maintenance Cycle 17	End of Treatment and Follow up 
Induction and Post Induction Cycles = 28 days (4 weeks)									
Maintenance Cycles = 84 days (12 weeks)		Day 1	Day 1 (±3)	Day 1 (±7)	Day 1 (±7)	Day 1 (±7)	Day 1 (±14)	Day 28 (±7)	Day 1
CORRELATIVE STUDIES									
Serum for Bone Turnover Markers 		X 	X 						X 

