**7.6 Post Induction Cycles 9-12 ( $\pm$  7 days)**

**NOTE:** ADT may continue for up to 2 years from randomization

- Laboratory tests D1 of each cycle:
  - PSA
  - Alkaline phosphatase
- Assessment of adverse events and concomitant medications. This may be done via email, phone call or medical record review

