### 7.10 End of Treatment (EOT) and Follow Up

The end of treatment/follow up column will be utilized for subjects that come off protocol therapy (radium-223 dichloride if randomized to that Arm and ADT) for toxicity or progression. If this occurs, subjects should have an end of treatment visit 30 days ( $\pm$  7 days) after discontinuation of protocol therapy. Subjects will then continue to be followed every 3 months for a total of 2 years from the date of randomization. Follow up may occur via phone call, email or other communication. If available by medical record review, alk phos, PSA, AE/concomitant medication should be obtained. Testing to be done at the EOT visit:

- Circulating tumor cell's (CTCs)
- Serum bone turnover markers
- Banking Samples: serum, plasma
- Alkaline phosphatase
- PSA

If a subject withdraws consent, he is deemed **“off study”**. “Off study” subjects will not be followed further.

A subject will be discontinued from the protocol specified therapy under the following circumstances:

- If there is evidence of radiologic disease progression or symptomatic deterioration despite castration range serum testosterone level ( $< 50$  ng/dL). Such subjects can go on to other treatment outside the study as clinically indicated including continuation or initiation of radium-223 dichloride therapy. They will remain on follow-up portion of the study for a total of 2 years from the date of randomization.
- If there is development of castration-resistant prostate cancer by PSA criteria in conjunction with castration range serum testosterone level ( $< 50$  ng/dL). Castration resistant prostate cancer is defined as two consecutive increases in PSA over the nadir PSA, at least two weeks apart **AND** an absolute increase of at least 2 ng/mL from the nadir PSA (or from baseline PSA if there was no drop in PSA after starting treatment). Discontinuation of bicalutamide may be attempted at the investigator's discretion in such cases and would NOT constitute going “off treatment”. If no response to bicalutamide discontinuation, such subjects may receive other treatment outside the study as clinically indicated including continuation or initiation of radium-223 dichloride therapy. They will remain on follow-up portion of the study for a total of 2 years from the date of randomization.

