#### Adverse Events

In the placebo-controlled phase 3 randomized clinical trial ALSYMPCA in subjects with metastatic castration-resistant prostate cancer with bone metastases, 600 subjects received intravenous injections of 50 kBq/kg (1.35 microcurie/kg) of Radium-223 dichloride and best standard of care and 301 subjects received placebo and best standard of care once every 4 weeks for up to 6 injections. Prior to randomization, 58% and 57% of subjects had received docetaxel in the Radium-223 dichloride and placebo arms, respectively. The median duration of treatment was 20 weeks (6 cycles) for Radium-223 dichloride and 18 weeks (5 cycles) for placebo. The

most common adverse reactions ( $\geq 10\%$ ) in subjects receiving radium-223 dichloride were nausea, diarrhea, vomiting, and peripheral edema. Grade 3 and 4 adverse events were reported among 57% of Radium-223 dichloride-treated subjects and 63% of placebo-treated subjects.

The most common hematologic laboratory abnormalities in Radium-223 dichloride-treated subjects ( $\geq 10\%$ ) were anemia, lymphocytopenia, leukopenia, thrombocytopenia, and neutropenia. Treatment discontinuations due to adverse events occurred in 17% of subjects who received Radium-223 dichloride and 21% of subjects who received placebo. The most common hematologic laboratory abnormalities leading to discontinuation for Radium-223 dichloride were anemia (2%) and thrombocytopenia (2%).

Adverse Events with Possible Relationship to Radium-223 dichloride		
Likely (>20%)	Less Likely ( $\leq 20\%$ )	Rare but Serious (<3%)
BLOOD AND LYMPHATIC SYSTEM DISORDERS		
Anemia	Neutropenia	
Lymphocytopenia	Pancytopenia	
Leukopenia		
Thrombocytopenia		
GASTROINTESTINAL DISORDERS		
Nausea		
Diarrhea		
Vomiting		
GENERAL DISORDERS AND ADMINISTRATION SITE CONDITIONS		
	Peripheral edema	
RENAL AND URINARY DISORDERS		
	Renal failure and impairment	

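### After a final radium-223 dose given at or after C8D1, no blood count is scheduled until C13D1, so silent cytopenia may be missed or under-graded

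*Combined protocol and SAP*

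**What the plan says.** Section 5.4 sets the start of radium-223: "Subjects randomized to this arm will begin treatment on C2D1". Doses are 28 days apart, up to six. Section 7.5 and the study calendar schedule a CBC at C8D1.

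Section 5.5.3 covers the case where "all 6 doses have not been administered by the 28 weeks' time-point". For those doses it says that "they may be administered later at the discretion of the site investigator provided laboratory parameters as outlined above are satisfied". It gives no outer time limit. It asks the site to record data on each late administration, including the dose, the date and the counts obtained within 3 days of it.

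Section 7.6 lists PSA and alkaline phosphatase on Day 1 of each of Cycles 9-12, and adds: "Assessment of adverse events and concomitant medications. This may be done via email, phone call or medical record review". The CBC row of the calendar is blank for these cycles. The next CBC is at C13D1 (7.7).

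In 7.10, the list under "Testing to be done at the EOT visit" has circulating tumor cells, bone turnover markers, banking samples, alkaline phosphatase and PSA. It has no CBC, and the calendar's EOT column has none.

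Section 12.7 describes toxicity within each arm by type, maximum grade and frequency.

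**The concern.** Section 5.5.3 permits radium-223 in a period for which 7.6 and the calendar schedule no hematologic follow-up. Two men in the same arm, each given six doses, are then observed differently. The man treated on schedule has a planned count 28 days after his last dose. The man who finishes late has a planned count only months later.

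This matters because the common hematologic abnormalities listed for radium-223 in section 10.1 are all reductions in blood counts. Such an abnormality can be graded only if a count is taken. Safety is the first secondary objective (2.2.1), and 11.1.1 counts abnormal laboratory findings as adverse events. Only the ADT+R arm receives radium-223, so only that arm's radium-related counts can be lost in this way.

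**Working it through.** **Inputs.** Radium-223 starts at C2D1 (5.4). Cycles last 28 days up to Cycle 12 (section 7 calendar). CBCs are scheduled at screening, Cycles 1-8, C13D1 and C17D28, but not in Cycles 9-12, Cycles 14-16 or at EOT (calendar, 7.2-7.10).

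**Formula.** With C1D1 as day 0, Cycle k Day 1 falls on day 28 × (k − 1). The gap is the day of the next scheduled CBC minus the day of the last dose.

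**The plan's own figure.** C8D1 = 28 × 7 = day 196, and 196 / 7 = 28 weeks. This matches the time-point in 5.5.3.

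**Days used.** C7D1 = 28 × 6 = 168. C8D1 = 196. C9D1 = 28 × 8 = 224. C13D1 = 28 × 12 = 336. Section 7.7 also describes C13D1 as 12 months from the start of ADT, so day 365 is shown as the alternative reading.

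| Last dose | Delay (days) | Gap if C13D1 is day 336 | Gap if C13D1 is day 365 |
|---|---|---|---|
| Day 168 (C7D1) | 0 | 196 − 168 = 28 | 28 |
| Day 182 | 14 | 196 − 182 = 14 | 14 |
| Day 196 (C8D1) | 28 | 336 − 196 = 140 | 365 − 196 = 169 |
| Day 224 (C9D1) | 56 | 336 − 224 = 112 | 365 − 224 = 141 |
| Day 252 | 84 | 336 − 252 = 84 | 365 − 252 = 113 |

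Visit windows of ±7 days shift these slightly.

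**What the table shows.** A delay of less than 28 days is harmless here, because the C8D1 CBC still follows the dose. The gap opens when the last dose falls at or after C8D1. A dose given on C8D1 is not covered by that day's CBC, because the count has to precede the dose (5.4, 6.2.2.1).

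**A late dose needs no unusual course.** Section 6.2.2 allows a delay of up to 56 days for inadequate counts, drug supply or dose interval. A single 28-day delay moves dose 6 to C8D1.

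**Comparison with the plan's own time scale.** Section 6.2.2.1 judges recovery over 56 days: "If there is no recovery to these values within 8 weeks after the last administration of radium-223 dichloride". Gaps of 112 and 140 days are 112 / 56 = 2.0 and 140 / 56 = 2.5 times that window, so a transient low could come and go unrecorded.

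**EOT.** A man who leaves all protocol therapy at a Day 1 visit in Cycles 3-8 has that visit's CBC, about 28 days after the previous dose. If he leaves before his next Day 1 visit, the plan schedules no count after his last dose, because the EOT draw omits it.

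**The case against.** The strongest reply is that the plan has other ways to find toxicity. The calendar footnotes allow extra CBCs at the investigator's discretion. Adverse events are reviewed in each of Cycles 9-12, recorded until 30 days after the last dose of study drugs, and followed to resolution if related (11.2.1). C13D1 has its own CBC. This stands, and it rules out saying that marrow toxicity after a late dose is simply missed. What remains is that these routes depend on symptoms, on discretion or on an event already found, whereas men treated on schedule get a count regardless.

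A reader might also infer that late-dosed men are those with the most vulnerable marrow. The documents do not support that. Doses can be late because of drug supply or dose interval (6.2.2), external beam radiation (5.9) or non-hematologic toxicity (6.2.2.2), and no frequencies are given. Men held for low counts have weekly CBCs and must meet the count criteria before the next dose (6.2.2.1). Those weekly counts do not close the gap, since nothing triggers them once no further dose is planned.

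Nor does 5.5.3 restrict recording to counts within 3 days of a dose. Its list is introduced as examples of what to record. It simply asks for no later count.

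The consequence is modest. Toxicity grades are described within each arm, the safety interim (12.3) uses related serious adverse events, and the primary endpoint is untouched. For scale, section 1.3 reports grade 3-4 anemia in 11%, neutropenia in 2% and thrombocytopenia in 4% in the phase 3 trial. Per 10 late-dosed men that is 10 × 0.11 = 1.1, 10 × 0.02 = 0.2 and 10 × 0.04 = 0.4 events. Those rates come from castration-resistant disease and are not specific to the period after the last dose, so they are indicative only.

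Finally, the calendar, 7.6 and 7.10 agree with one another. The mismatch is between them and the late dosing that 5.5.3 permits.

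**Conclusion.** The point holds in limited form. When the last dose falls at or after C8D1, the wait for a scheduled CBC rises from 28 days to 140 days (dose at C8D1) or 112 days (dose at C9D1), or to about 169 and 141 days on the calendar-month reading. As a result, asymptomatic or transient cytopenia after a late final dose may be missed or under-graded in the 12.7 maximum-grade summary for ADT+R. The missing CBC at EOT is secondary. It affects only men who leave all protocol therapy before their next Day 1 visit; men who stop radium-223 but remain castrated stay on protocol therapy (7.10) and keep the regular CBC schedule.

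The result rests on 28-day cycles and on sites drawing only what is scheduled. The documents do not allow the number of affected men to be estimated, and no claim is made that they are at higher marrow risk.

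**What to change.** Reconcile 5.5.3 with the calendar, 7.6 and 7.10, so that hematologic data after a late last dose are collected comparably to those after an on-schedule dose:

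- In the calendar and 7.6, when the last radium-223 dose is given at or after C8D1, add a CBC to the PSA/ALP sample already drawn at the next Day 1 visit in Cycles 9-12. For a last dose at C8D1 or C9D1 this restores the 28-day interval (C9D1 − C8D1 = 224 − 196 = 28). For a dose between Day 1 visits the interval is shorter.
- In the calendar and 7.10, add a CBC to the EOT blood draw.
- In 12.7, state that these counts enter the maximum-grade summary.

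This is safety data collection and changes no dose, hold or stopping rule. It costs one routine test on blood already being taken, for a minority of men, plus a calendar footnote. It adds no visit.

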### 5.6 PSA Assessments

PSA values will be assessed:

- PSA obtained prior to initiating androgen deprivation therapy, should be used as the baseline PSA. For subjects in the early induction group, if a baseline PSA prior to initiation of ADT is not available, the baseline PSA will be considered the value obtained prior to randomization.
- Prior to randomization then
- Day 1 of every Cycle through Cycle 12 then
- Every 3 months for the following year
- More frequent PSA monitoring as clinically indicated is acceptable.

### 5.7 Pre-medication

Institutional standards should be followed for hydration and pre-medications for LHRH agonists or antagonists. No pre-medications are needed prior to the first dose of radium-223 dichloride. Anti-emetics may be used subsequently as clinically indicated.

### 5.8 Concomitant Medications

The use of supportive care medications is allowed according to institutional standards. We strongly recommend supplemental calcium 1200 mg daily and Vitamin D3 1000 IU daily.

However, certain medications are specifically disallowed.

- Five-alpha reductase inhibitors (e.g. finasteride and dutasteride) are not permitted.
- Other excluded therapies include ketoconazole, aminoglutethimide, abiraterone acetate, enzalutamide (MDV3100), diethylstilbestrol (DES), and other estrogen preparations.
- Cytotoxic chemotherapy is not allowed during protocol specified therapy.

## 5.9 Supportive Care

- Institutional standards should be followed for hydration and pre-medications.
- The use of packed red blood cell transfusions is allowed as clinically indicated per institutional guidelines or at investigator's discretion but must be clearly documented in the source documents.
- Palliative external beam radiation therapy for prostate cancer during protocol specified therapy is allowed as clinically indicated. Radium-223 dichloride doses must be held during external beam radiation therapy and may resume after a minimum of 7 days after completion of external beam radiation if hematological laboratory parameters are adequate (see section 5).
- Palliative external beam radiation therapy can start without a minimum time interval after a radium-223 dose as clinically indicated.
- Colony stimulating factors (e.g. G-CSF or GM-CSF) are not allowed during protocol specified therapy.
- Prolonged use of systemic corticosteroids for prevention of allergic reactions is discouraged because of their potential to cause and exacerbate hyperglycemia. Intermittent use of corticosteroids is permitted.

